13.2 Laboratory safety variables

Laboratory safety variables (biochemistry and haematology) to be analyzed are presented in table 1 below. Descriptive statistics and the frequency and percentage of absolute values below, within and above the reference range will be tabulated for the safety laboratory variables at D0 (baseline), D1, D2, D3, D4, D5, D6, D9, D13 and D30. Descriptive statistics will include mean, median, standard deviation (SD), minimum and maximum.

In addition, shift tables (within, below and above the normal range) will be provided for each parameter in relation to the maximum change from baseline from D0 over the complete 30-day follow-up period.

Table 1. Laboratory Variables

Biochemistry	Haematology Includes coagulation
Alanine transaminase (ALAT)	Hemoglobin
Alkaline phosphatase (AFOS)	Leucocyte differential count (absolute)
Aspartate transaminase (ASAT)	Mean cell volume
Bicarbonate	Platelet count
Lactate	Red cell count
pH	White cell count
Bilirubin	
Calcium	
Creatinine	
Potassium	
Sodium (blood gas value acceptable)	

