5.8 Guidance on medications to be administered/patient management for expected Adverse Events

Recombinant Human IFN beta-1a has been widely used in man for the treatment of multiple sclerosis and is considered safe. Some adverse effects are anticipated. Most common are changes in blood biochemistry of liver function, i.e. ALAT, ASAT, AFOS. A slight elevation in liver enzymes is often seen, and needs to be followed. These changes usually subside after cessation of treatment. Most common severe adverse effects are fever, tachycardia and rigor, since the drug substance is to some extent pyrogenic by nature. These adverse effects mostly occur shortly after administration and cease after treatment. These adverse effects may be managed with otherwise suitable medication depending on the symptom: paracetamol or other antipyretics for fever, beta blockers for tachycardia, benzodiazepines for rigor or even propofol sedation in the ICU setting.

Few adverse effects are expected after the treatment period since, as shown in the FPCLI001 study, FP-1201 activity decreases significantly within few days after administration, according to MxA measurements. Thus, the IMP will be washed out before discharge from the hospital. For more information on the anticipated effects of the FP-1201-lyo treatment see the **Investigators' Brochure**.

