6.3.2 Laboratory Variables

The biochemistry and haematology analysis will be performed at the hospital laboratories of the individual Investigator sites. These analyses are mostly included in the standard care of RAAA patients. Copies of laboratory accreditation and relevant

reference ranges will be provided to the Sponsor or representative prior to the analysis of the first patient sample at that site.

The laboratory variables measured in the study will be as detailed in Table 2.

Blood samples for determination of biochemistry and haematology will be taken at pre-dose on D0 (baseline value), D1, D2, D3, D4, D5, D6, D9, D13 and D30 (or on a particular date if a patient is discharged from initial operating hospital or discontinues from the study after D6 but prior to D30), as detailed in the study flow charts in Tables 5 & 6. Patient is not invited to laboratory visit, once discharged from hospital, except on D30 for assessment of NABs. The date and time of collection will be recorded in the eCRF.

Table 2: Laboratory Variables

Biochemistry	Haematology Includes coagulation	Other
Alanine transaminase (ALAT) Alkaline phosphatase (AFOS) Aspartate transaminase (ASAT) Bicarbonate Lactate pH Bilirubin Calcium Creatinine Potassium Sodium (blood gas value acceptable)	Haemoglobin Leucocyte differential count (absolute) Mean cell volume Platelet count Red cell count White cell count	Pregnancy test

Total volume of blood required for biochemistry and haematology samples per patient are shown below in Table 3.

Table 3: Total Volume of Blood required for Biochemistry/Haematology Samples

Assessment	Number of Samples	Per Sample Volume (mL)	Total Volume (mL)
Biochemistry	9	6	56
Haematology	9	9	81
Pregnancy test	1	4	4
			141

6.3.3 *Vital Signs*

Vital signs are recorded at D0 pre-dose (baseline) and continuously during ICU stay, and at least daily during hospital care. Reporting points D0 pre-dose (0 hrs), D1, D2, D3, D4, D5, D6, D9, D13 and D30 (or on a particular date if a patient withdraws from the study after D6 but prior to D30), as detailed in the study flow charts. The date and time of collection of each parameter will be recorded in the eCRF.

Vital sign variables include:

- Blood pressure (BP) (mmHg): to be recorded intra-arterially or using a device with an appropriate cuff size for the patient.
- Heart rate (HR) (bpm): measured as per clinical practice on each ICU

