13.1 Adverse events

All recorded adverse events will be coded according to the Medical Dictionary for Regulatory Activities (MedDRA). Treatment emergent adverse event (TEAE) is defined as an AE that begins or worsens in severity after at least one dose of study drug has been administered. Non-treatment emergent AEs are listed only.

TEAEs will be summarized using frequency and subject based tables. TEAEs will be tabulated by treatment group, system organ class (SOC), preferred term (PT), causality and severity. For analysis purposes, each subject will also be categorized by the maximum severity reported for a given TEAE and these will be tabulated by maximum severity. TEAEs will be summarized separately for treatment period (D1-D5) and short-term follow-up period (D6-D30). TEAEs are not collected, and therefore not reported, during the mid-term follow-up.

Serious adverse events (SAEs) and AEs leading to discontinuation will be summarized by treatment groups. All deaths up to D90 are reported as SAEs.

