13.3 Other safety variables

Other safety variable to be analysed are vital signs (body temperature, blood pressure, heart rate) and physical examination.

Vital signs data is summarized by treatment groups separately at D0, D1, D2, D3, D4, D5, D6, D9, D13 and D30. Absolute values and changes from baseline are both summarized. In addition, the maximum change from baseline over the 30-day follow-up period will be calculated for each patient and summarized. Vital signs summaries will be in terms of mean, median, SD, minimum and maximum.

Physical examination covering all the major organ systems will be performed at screening and D30. These will be summarized by treatment groups and visits using frequency and percentage of normal/abnormal observations. In addition, shift tables will be provided describing the change from screening to D30.

14 Completion and premature discontinuation

Completion and premature discontinuation will be listed. The reasons for premature discontinuation will be presented.

15 Deviations from the analyses planned in the study protocol

Study was discontinued after the first Interim analysis. Due to the early discontinuation, the planned O'Brien and Fleming correction will not be applied to the primary analysis. Instead, the standard p-value of less than 0.05 will be considered statistically significant.

Due to low number of accrued patients, the center effect was not further explored in the analyses. Analysis of study centers was limited to summary statistics for baseline information.

Due to the early discontinuation of the study, the pharmacoeconomic endpoints (see section 12.3.2) will not be analysed.

There are no other major deviations in the statistical analysis plan from the analyses planned in the study protocol.

16 Execution of statistical analyses

Statistical analyses will be performed by [REDACTED].

17 Hardware and software

[figure not shown]
Statistical analysis, tables and patient data listings will be performed with SAS[®] version 9.4 or later for Windows (SAS Institute Inc., Cary, NC, USA).

18 References

Clinical Study Protocol (FP1CLO006), Final Protocol version 05 (16 April 2019), Faron Pharmaceuticals Ltd.

19 Appendices

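### Cheap improvement: the planned biochemistry summary tables do not count patients per arm by how high liver values rose

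*SAP*

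**What the plan says.** On adverse effects, protocol 5.8 states: "Most common are changes in blood biochemistry of liver function, i.e. ALAT, ASAT, AFOS". It adds that slight elevations are often seen and need to be followed, and then: "These changes usually subside after cessation of treatment".

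For laboratory values SAP 13.2 has three elements, matching Tables 14.3.9.1 to 14.3.9.3 for biochemistry:

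- mean, median, SD, minimum and maximum at D0 to D6, D9, D13 and D30;
- counts by range at the same days: "Descriptive statistics and the frequency and percentage of absolute values below, within and above the reference range will be tabulated for the safety laboratory variables";
- one across-visit summary at the maximum change from baseline: "shift tables (within, below and above the normal range) will be provided for each parameter".

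Protocol 8.4 has these laboratory statistics tabulated by treatment group. It plans no grading of values either.

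Elsewhere the SAP does keep a per-patient maximum. For adverse events (13.1), "each subject will also be categorized by the maximum severity reported for a given TEAE". For vital signs (13.3), "the maximum change from baseline over the 30-day follow-up period will be calculated for each patient and summarized".

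SAP section 9 provides for by-subject listing of all data, and Listing 16.2.29 covers biochemistry.

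**The concern.** The one laboratory effect that the protocol singles out is summarised only by day, or by patient at three levels. Below, within and above range says nothing about height once a value is above. The daily maximum shows that someone was high on that day, but not whether it was the same patient as the day before.

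Safety is part of the primary objective and is also a secondary objective. From the summary tables alone, a reader could not state how many patients in each arm had a marked rise, or how many had ALAT or ASAT raised together with bilirubin. For the drug's named laboratory effect, those are natural questions to ask of a safety report.

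**Working it through.** The plan gives no figure to reproduce here. The check is by construction: can data sets with different numbers of markedly raised patients give identical planned summaries?

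**Inputs.** 35 evaluable patients at the first interim (SAP sections 2 and 8) and 2:1 allocation (protocol 4.6.1): 35 × 2/3 = 23.3, so about 23 active. The actual split is not given. Assumed: complete values on D1 to D6, every patient within range at D0, and the same values on D9, D13 and D30 in every version. All values are multiples of the upper limit of normal (ULN).

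**Values each day.** One value of 8.0, and 22 values at 1.20, 1.35, ..., 4.35 (steps of 0.15).

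- Mean: 22 × (1.20 + 4.35)/2 = 61.05; (61.05 + 8.00)/23 = 3.00.
- Median (12th value): 1.20 + 11 × 0.15 = 2.85.
- SD 1.45, minimum 1.2, maximum 8.0, above range 23/23.
- Shift table: within to above, 23/23.

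**Who holds the 8.0.** None of the summaries above changes between these rows:

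| Assignment of the daily 8.0 | Patients with peak above 5 × ULN |
|---|---|
| 1 patient, six days | 1/23 = 4.3% |
| 2 patients, three days each | 2/23 = 8.7% |
| 3 patients, two days each | 3/23 = 13.0% |
| 6 patients, one day each | 6/23 = 26.1% |

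Exact 95% intervals are 0.1 to 21.9% for 1/23 and 10.2 to 48.4% for 6/23.

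**General bound.** If k_d patients are high on day d, the number of patients ever high lies between max(k_d) and the smaller of n and the sum of the k_d. Here k_d = 1 on six days, so between 1 and 6.

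**When the shift table does separate the cases.** Take 24 patients, with either one patient at 10 × ULN on all of D1 to D6, or six patients at 10 × ULN on one day each. If everyone else is at 1.5 × ULN on those days, the shift table reads 24/24 within to above in both cases. If everyone else stays within range, it reads 1/24 against 6/24. The ambiguity therefore requires most patients to be above range.

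**What the planned tables would show anyway.** Put six of the 23 at 8.0 on every day and draw the other 17 from the same list. With the 17 lowest, the mean is (40.80 + 48.00)/23 = 3.86 and the SD 2.60. With the 17 highest, the mean is (53.55 + 48.00)/23 = 4.42 and the SD 2.27. Against 3.00 and 1.45, sustained rises in several patients are visible.

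**Raised baseline.** If maximum change is read as absolute change, a patient at 6 × ULN at D0, 9 × at peak and 0.9 × at D30 has changes of 3 and 5.1. The shift table would then file this patient as within range.

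**Denominator.** The 23 derives from FAS-E, which excludes deaths within 36 hours, whereas laboratory tables use FAS-S. At the planned 15% early-death rate, 35/0.85 = 41.2 treated, and 41.2 × 2/3 gives about 27 active. The range becomes 1/27 = 3.7% to 6/27 = 22.2%. The argument does not change.

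**The case against.** The strongest case against is that the plan already covers what the protocol expects. The effect named in protocol 5.8 is often a slight elevation, and the within-to-above shift counts that per patient. The protocol's chosen safety measure (3.2.2) is clinically significant treatment-emergent events, including those arising from laboratory data. Rises that need significant intervention, stop the drug or concern the investigator can become adverse events (6.3.1.3), and these are tabulated per patient by maximum severity. Listing 16.2.29 lets anyone trace values by hand, which is easy in a study this small. SAP 13.2 also goes beyond protocol 8.4 by adding D9, D13 and the range counts.

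Most of this stands. The adverse-event route is only a partial substitute. Disease-associated laboratory findings are reported only if the investigator judges them more severe than expected (6.3.1.3.4), and severity is graded by effect on function (6.3.1.3.2), so a severity count is not a count by enzyme level. The listing holds the answer but does not summarise it.

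A reader might infer that marked rises cannot be traced to patients at all, or that the plan would conceal a liver signal. The documents do not support either. The listings identify each patient, a sustained rise in several patients would move the daily mean and SD, and the daily maximum would show any extreme value.

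**Conclusion.** The point holds as a limit of the summary tables. They do not count patients per arm by height of rise, and when most patients are above range they cannot separate one sustained marked rise from several brief ones.

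The range of 1 to 6 patients is illustrative and not a forecast. It rests on an assumed 23-patient arm, complete sampling, all patients within range at D0, and all above range on every treatment day. Because protocol 5.8 says the changes usually subside once treatment stops, rises lasting several days are more plausible than six one-day spikes, so the realistic ambiguity lies nearer 1 to 3 patients. The intervals are wide and any such counts would be descriptive.

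This is an optional improvement and not an error. No test, stopping rule or decision depends on it.

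**What to change.** In SAP 13.2, keep the planned tables and add one descriptive table by arm (for example 14.3.9.4) in FAS-S for ALAT, ASAT, AFOS and bilirubin. Divide each value by the local laboratory's upper limit of normal, and show:

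- (a) the number and percentage of patients whose highest post-dose value up to D30 exceeds 1, 3, 5 and 10 times the limit, by D0 pre-dose category;
- (b) the number of patients with ALAT or ASAT above 3 times and bilirubin above 2 times the limit on the same scheduled sampling day;
- (c) the number of post-dose samples per patient, at most 9 (D1 to D6, D9, D13, D30).

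All cut-offs, including the 2-times bilirubin cut, are proposed here and do not come from the documents. Item (a) also handles the raised-baseline case. Item (c) is needed because a peak depends on how long the patient was sampled, and sampling is cut short by death, transfer or discharge: "Patient is not invited to laboratory visit, once discharged from hospital, except on D30 for assessment of NABs".

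The cost is a little programming. The values are already collected, and under protocol 6.3.2 the local "reference ranges will be provided to the Sponsor or representative prior to the analysis of the first patient sample at that site". No new samples, patients or procedures are needed. The drawback is small counts that can only be read descriptively and against length of sampling.

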13.3 Other safety variables

Other safety variable to be analysed are vital signs (body temperature, blood pressure, heart rate) and physical examination.

Vital signs data is summarized by treatment groups separately at D0, D1, D2, D3, D4, D5, D6, D9, D13 and D30. Absolute values and changes from baseline are both summarized. In addition, the maximum change from baseline over the 30-day follow-up period will be calculated for each patient and summarized. Vital signs summaries will be in terms of mean, median, SD, minimum and maximum.

Physical examination covering all the major organ systems will be performed at screening and D30. These will be summarized by treatment groups and visits using frequency and percentage of normal/abnormal observations. In addition, shift tables will be provided describing the change from screening to D30.

14 Completion and premature discontinuation

Completion and premature discontinuation will be listed. The reasons for premature discontinuation will be presented.

15 Deviations from the analyses planned in the study protocol

Study was discontinued after the first Interim analysis. Due to the early discontinuation, the planned O'Brien and Fleming correction will not be applied to the primary analysis. Instead, the standard p-value of less than 0.05 will be considered statistically significant.

Due to low number of accrued patients, the center effect was not further explored in the analyses. Analysis of study centers was limited to summary statistics for baseline information.

Due to the early discontinuation of the study, the pharmacoeconomic endpoints (see section 12.3.2) will not be analysed.

There are no other major deviations in the statistical analysis plan from the analyses planned in the study protocol.

16 Execution of statistical analyses

Statistical analyses will be performed by [REDACTED].

17 Hardware and software

[figure not shown]
Statistical analysis, tables and patient data listings will be performed with SAS[®] version 9.4 or later for Windows (SAS Institute Inc., Cary, NC, USA).

18 References

Clinical Study Protocol (FP1CLO006), Final Protocol version 05 (16 April 2019), Faron Pharmaceuticals Ltd.

19 Appendices

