8.4 Evaluation of safety

All patients who receive a minimum of one administration of study medication are included in the safety analysis.

Adverse Events

Treatment Emergent Adverse Effects (TEAEs) and SAEs are classified according to the Medical Dictionary for Regulatory Activities (MedDRA) SOC and the preferred term. The incidence of these events will be summarised by treatment group in tables which will also include information on severity and relationship to study medication. These summaries will be based on the Safety Set. The frequency of complications is summarised by treatment groups in terms of counts.

Vital Signs

Vital signs data (BP, HR and temperature) is summarised by treatment group separately at D0, D1, D2, D3, D4, D5, D6, D9, D13 and D30. The maximum change from baseline over the 30-day follow-up period will be calculated for each patient and summarised.

Vital signs summaries will be in terms of mean, median, standard deviation (SD), minimum and maximum.

Clinical Laboratory Parameters

Descriptive statistics (mean, median, SD, minimum and maximum) for biochemistry and haematology will be obtained and tabulated by treatment group at D0, D1, D2, D3, D4, D5, D6 and D30. Descriptive statistics (mean, median, SD, minimum and maximum).

Shift tables (within, below and above the normal range) will also be provided for each parameter in relation to the maximum change from baseline from D0 over the complete 30-day follow-up period.

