Table 14.3.5.2	TEAEs during short-term follow-up period by causality (FAS-S)
Table 14.3.5.3	TEAEs during short-term follow-up period by severity (FAS-S)
Table 14.3.5.4	TEAEs during short-term follow-up period by maximum severity (FAS-S)
Table 14.3.5.5	TEAEs during short-term follow-up period by causality and severity (FAS-S)
Table 14.3.5.6	TEAEs during short-term follow-up period by causality and maximum severity (FAS-S)
Table 14.3.6	Listing of other adverse events (FAS-S)
Table 14.3.7	TEAEs leading to discontinuation (FAS-S)
Table 14.3.8	Serious TEAES (FAS-S)
Table 14.3.9.1	Biochemistry - Descriptive statistics (FAS-S)
Table 14.3.9.2	Biochemistry - Categorical analysis (FAS-S)
Table 14.3.9.3	Biochemistry - Shift tables (FAS-S)
Table 14.3.10.1	Haematology - Descriptive statistics (FAS-S)
Table 14.3.10.2	Haematology - Categorical analysis (FAS-S)
Table 14.3.10.3	Haematology - Shift tables (FAS-S)
Table 14.3.11.1	Vital signs - Descriptive statistics (FAS-S)
Table 14.3.11.2	Vital signs - Change from baseline (FAS-S)
Table 14.3.11.3	Vital signs - Maximum change from baseline (FAS-S)
Table 14.3.12.1	Physical examination (FAS-S)
Table 14.3.12.2	Physical examination - Shift from screening to D30

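### Maximum change from baseline has no stated direction, and any single value per patient drops either rises or falls from the worst-case safety tables

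*SAP*

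**What the plan says.** **Vital signs.** SAP 13.3 states that "the maximum change from baseline over the 30-day follow-up period will be calculated for each patient and summarized". Protocol 8.4 has the same sentence: "The maximum change from baseline over the 30-day follow-up period will be calculated for each patient and summarised". The table plan in SAP 19.3 gives this one output, Table 14.3.11.3, and lists no companion table for decreases.

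**Laboratory variables.** SAP 13.2 has no numeric summary of maximum change. It uses the term to define the shift tables: "shift tables (within, below and above the normal range) will be provided for each parameter in relation to the maximum change from baseline". These are Tables 14.3.9.3 (biochemistry) and 14.3.10.3 (haematology). Protocol 8.4 words the shift tables in the same way.

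**What surrounds them.** Vital signs are also reported at D0 to D6, D9, D13 and D30: "Absolute values and changes from baseline are both summarized", and "Vital signs summaries will be in terms of mean, median, SD, minimum and maximum". For the laboratory variables on the same days, the "frequency and percentage of absolute values below, within and above the reference range will be tabulated". SAP 9 plans by-subject listings of all data.

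None of these sections says whether maximum change is signed, absolute or the worst direction for each variable. Elsewhere the plan does fix a direction: adverse events are categorised by maximum severity (SAP 13.1), and SOFA uses the worst daily value (protocol 7.3).

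**The concern.** A worst-case table should show how far each patient moved in the harmful direction. For blood pressure, haemoglobin, platelets and white cells that direction is often down. A single undirected maximum leaves the programmer to choose, and the choice decides whether falls appear in the table.

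The by-visit tables do not replace a per-patient summary:

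- A by-visit minimum is one patient's value on one day. It does not show how many patients had a deep fall.
- By-visit counts can include the same patient on several days, so they cannot be added up to a number of patients.
- Denominators shrink as patients die or leave, because assessments before D30 are made only in the operating hospital (protocol 7.5).
- By-visit laboratory tables cover absolute values only. The shift table is the one planned laboratory summary relative to baseline.

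Safety is part of the primary objective (protocol 2.1). The study stopped after an interim analysis of 35 evaluable patients (SAP 2), so the safety tables will rest on few patients.

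**Working it through.** The documents give no figure that depends on this definition, so there is none to reproduce. The check compares what each reading of the term would report. Only the nine post-baseline reporting days (D1 to D6, D9, D13, D30) come from the plan. All SDs, profiles and reference ranges below are assumptions.

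**1. Single-patient profiles.** Assumed ranges are platelets 150 to 400 and white cells 4 to 11, in the usual units.

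| Profile | Signed maximum | Largest absolute change, sign kept | Largest decrease |
|---|---|---|---|
| Platelets 180, lowest 60, later 190 | +10, within | -120, below | -120, below |
| White cells 8, lowest 2.5, later 9 | +1, within | -5.5, below | -5.5, below |
| Systolic pressure 120, lowest 80, later 135 | +15 | -40 | -40 |
| Platelets 180, lowest 60, rebound 420 | +240, above | +240, above | -120, below |

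The signed maximum misses the fall in all four. The absolute reading keeps it in the first three and loses it in the fourth, where the rebound (420 - 180 = 240) exceeds the fall (180 - 60 = 120). The by-visit laboratory table would still count the three laboratory patients below range at 6, 4 and 5 visits respectively. The by-visit change table would still contain the -40 mmHg.

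**2. One fall per patient.** Take nine independent readings with SD 15 mmHg, a baseline with the same mean and SD, and one 60 mmHg fall on a random visit in every patient.

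- Signed maximum, no fall: the expected maximum of nine standard normals is 1.485, so the mean is 1.485 × 15 = 22.3 mmHg.
- Signed maximum, with the fall: about eight readings still compete, giving 1.424 × 15 = 21.4 mmHg. The table moves by about 0.9 mmHg.
- Share of patients with a positive signed maximum: 9/10 = 90% without the fall and about 8/9 = 89% with it. The two are almost equal, so this share tells the reader nothing about the fall.
- Largest absolute change, sign kept (simulated): mean about 0 without the fall and about -50 mmHg with it. With the fall the median is about -60 mmHg and 87% of values are negative.
- Largest decrease (simulated): mean -22.3 mmHg without the fall and -60.1 mmHg with it, a movement of 37.8 mmHg.

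**3. A sustained fall in one arm.** This simulation used 200,000 patients per arm, within-patient correlation from 0 to 0.6, and a fall on D1 to D5 in one arm only. Differences between arms in the mean per-patient value, in SDs of a single reading:

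| Fall | Signed maximum | Largest absolute change, sign kept | Largest decrease |
|---|---|---|---|
| 1 SD | -0.27 to -0.36 | -1.19 to -1.21 | -0.73 to -0.81 |
| 2 SD | -0.29 to -0.44 | -2.45 to -2.50 | -1.68 to -1.80 |

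The signed maximum hardly grows when the fall doubles. The other two summaries do respond.

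**The case against.** The strongest reply is that a reader might infer the plan hides falls in blood pressure, platelets and white cells. The documents do not support that.

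- **Signed is only one reading.** Neither document says so, and a shift table with a below category fits a change in either direction at least as well. Under the absolute reading with the sign kept, the 60 mmHg fall is plainly visible. The idea that rises and falls simply cancel in the group mean fails in that scenario, and the median, SD, minimum and maximum are planned as well.
- **Falls appear elsewhere.** By-visit vital-sign tables give change from baseline with its minimum. Laboratory tables count values below range at each visit. Treatment-emergent adverse events run to D30 (protocol 6.3.1.2), and clinically significant laboratory or vital-sign abnormalities can qualify as adverse events (protocol 6.3.1.3.4). So these are not the only summaries covering the 30 days.
- **Attrition is a limited argument.** The maximum draws on the same reporting days as the by-visit tables. A fall on D2 in a patient who dies on D3 is already in the D2 table.

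All of this stands, and it confines the point to the per-patient worst-case display. It does not rescue a single value. The absolute reading still loses a fall followed by a larger rebound, and one shift cell per patient cannot record both a low and a high excursion.

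**Conclusion.** The point holds as a minor improvement to descriptive safety output. The direction of maximum change is undefined, and no single-value reading shows both rises and falls. Under the signed reading the loss is nearly complete: about 0.9 mmHg of movement for a 60 mmHg fall in every patient. Under the absolute reading it is confined to patients whose rise exceeds their fall and to those with excursions in both directions.

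The gap matters most for blood pressure. Vital signs have no below-range category in the plan, so Table 14.3.11.3 is the only planned per-patient worst-case summary of them. For platelets and white cells the point rests on the shift tables in SAP 13.2, and the below-range counts soften it.

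The sizes quoted depend on assumed SDs, assumed profiles and, in the mmHg example, independent readings. The qualitative result does not depend on them. The primary analysis, sample size and error rate are not affected.

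**What to change.** In SAP 13.3 and Table 14.3.11.3, replace the single maximum change with two summaries for each vital sign: the largest increase and the largest decrease from baseline over the 30 days.

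In SAP 13.2 and Tables 14.3.9.3 and 14.3.10.3, produce two shift tables for each laboratory variable: baseline category to the category of the lowest post-baseline value, and baseline category to that of the highest.

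Record the change from the protocol 8.4 wording in SAP 15. The cost is a few extra columns or tables. No new data are needed, and SAP 8 places database lock still ahead.
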